8 CONVENTIONS

8.1 Calculations of Key Measures

8.1.1 *Evaluation of PASI*

The PASI is a grading system used for the evaluation of the severity of psoriatic lesions and their response to treatment. The PASI produces a numeric score that can range from 0 to 72. The severity of a subject's disease is calculated as described below:

In the PASI system, the body is divided into 4 regions: the head (h), trunk (t), upper extremities (ux) and lower extremities (lx), which account for 10%, 30%, 20%, and 40% respectively of the total body surface area (BSA). Each of these areas are evaluated for erythema, induration and scaling, which are rated on a scale from 0 to 4.

The scoring system for the signs of disease (erythema, in duration and scaling) is below:

- 0 = none
- 1 = slight
- 2 = moderate

3 = severe

4 = very severe

The scoring system for estimating the area of involvement for psoriatic lesions is outlined below:

0 = no involvement

1 = 1% to 9% involvement

2 = 10% to 29% involvement

3 = 30% to 49% involvement

4 = 50% to 69% involvement

5 = 70% to 89% involvement

6 = 90% to 100% involvement

To aid in the area assessments, the following conventions are followed:

- a. the neck is considered part of the head
- b. the axilla and groin are considered part of the trunk
- c. the buttocks are considered part of the lower extremities

The PASI formula is:

$$\text{PASI} = 0.1(E_h + S_h + I_h)A_h + 0.3(E_t + S_t + I_t)A_t + 0.2(E_{ux} + S_{ux} + I_{ux})A_{ux} + 0.4(E_{lx} + S_{lx} + I_{lx})A_{lx}$$

8.1.2 Evaluation of sPGA

The sPGA is used to determine the subject's psoriasis lesions overall at a given time point. Overall lesions will be graded for induration, erythema, and scaling based on the scales below. The sum of the 3 scales will be divided by 3 to obtain a final PGA score.

Induration (I) (averaged over all lesions; use the National Psoriasis Foundation Reference card for measurement)

0 = no evidence of plaque elevation

1 = minimal plaque elevation, = 0.25 mm

2 = mild plaque elevation, = 0.5 mm

3 = moderate plaque elevation, = 0.75 mm

4 = marked plaque elevation, = 1 mm

5 = severe plaque elevation, = 1.25 mm or more

Erythema (E) (averaged over all lesions)

0 = no evidence of erythema, hyperpigmentation may be present

1 = faint erythema

- 2 = light red coloration
- 3 = moderate red coloration
- 4 = bright red coloration
- 5 = dusky to deep red coloration

Scaling (S) (averaged over all lesions)

- 0 = no evidence of scaling
- 1 = minimal; occasional fine scale over less than 5% of the lesion
- 2 = mild; fine scale dominates
- 3 = moderate; coarse scale predominates
- 4 = marked; thick, nontenacious scale dominates
- 5 = severe; very thick tenacious scale predominates

Add $I + E + S / 3 =$ (Total Average)

Physician's Static Global Assessment based upon above Total Average

- 0 = Cleared, except for residual discoloration
- 1 = Minimal - majority of lesions have individual scores for $I + E + S / 3$ that averages 1
- 2 = Mild - majority of lesions have individual scores for $I + E + S / 3$ that averages 2
- 3 = Moderate - majority of lesions have individual scores for $I + E + S / 3$ that averages 3
- 4 = Marked - majority of lesions have individual scores for $I + E + S / 3$ that averages 4
- 5 = Severe - majority of lesions have individual scores for $I + E + S / 3$ that averages 5

Note: Scores should be rounded to the nearest whole number. If total ≤ 1.49 , score = 1; if total ≥ 1.50 , score = 2.

8.2 Baseline Measures

The baseline value is the last assessment taken prior to the first dose of study medication. In general, baseline value is the assessment taken on study Day 1 before the administration of study medication. If a measurement on Day 1 is missing, the last assessment taken at the screening period prior to the first dose of study medication will be used.

8.3 Missing Measurements

8.3.1 Imputation of Missing Data for Binary Variables

This imputation is applicable for all binary variables (PASI-50, PASI-75, PASI-90, PASI-100, sPGA score of 0/1).

If the response cannot be assessed due to missing data or a subject's early discontinuation, the following conventions will be implemented in a sequence:

- Any subject who prematurely discontinues the trial during the treatment period after receiving study medication will have data imputed as non-responder at all scheduled protocol visits subsequent to the point of discontinuation up to the end of the treatment period.
- If for some reason the binary variable still cannot be determined, including the case where baseline data is missing, then the value will be set to non-responder.

Efficacy data (PASI-50, PASI-75, PASI-90, PASI-100, sPGA score of 0/1) will be presented after imputation; and the number of the subjects with missing efficacy measures in each treatment group will be provided.

For listings, missing responses will be presented as missing.

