3 INVESTIGATIONAL PLAN

3.1 Study Design and Duration

This is a 12 week, multi-center, randomized double-blind, placebo-controlled, parallel-group multiple oral dose study in subjects with moderate to severe psoriasis. Subjects will be randomly assigned to receive BMS-986165 (3mg Q2D, 3mg QD, 3mg BID, 6mg BID, 12mg QD) or placebo. Subjects will undergo screening evaluations to determine eligibility within 28 days prior to administration of study medication.

This will be an outpatient study. Subjects will receive BMS-986165 or placebo capsules to be taken at home. Subjects will be provided by the Investigator Site with enough capsules to cover the treatment interval between study visits beginning on Study Day 1. Additional capsules covering the treatment interval between study visits should be supplied by the Investigator Site during each follow up visit. To facilitate PK analyses, certain doses of BMS-986165 or placebo capsules will be administered in the clinic (see [Section 4.5](#)).

[figure not shown]
Subjects will be reporting to the clinic for study visits on study Days 1, 8, 15, 29, 57, 85 and 115.

Physical examinations, clinical disease activity assessments (Psoriasis Area and Severity Index [PASI], Body Surface Area assessment [BSA], static Physician's Global Assessment sPGA), vital sign measurements, PK evaluations, clinical laboratory evaluations, ECG, skin biopsies, subject reported quality of life measures (DLQI), and PD evaluations will be performed at selected times throughout the dosing interval. Adverse events will be recorded and assessed by the Investigator (or designee as documented in the DOA) at study visits and throughout the study period. Subjects will be required to return to the clinic for additional (unscheduled) safety follow up visits as deemed necessary by the investigator.

Since BMS-986165 is a novel investigational agent with immunomodulatory effects, immunosuppressant agents will be discontinued prior to dosing in order to maximize subject safety. Further, in order to determine whether BMS-986165 exerts a potent anti-psoriatic effect in the absence of background therapy, participation requires that subjects discontinue therapy (with the exception of topical emollients for symptomatic relief) prior to dosing as described in [Sections 3.4.1](#).

The study design schematic is presented in [Figure 3.1-1](#).

Figure 3.1-1: Study Design Schematic

Q2D=every other day, QD=every day, BID=twice daily

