3.6 Post Study Drug Follow up

In this study, PASI-75 is a key endpoint of the study. Post study follow-up is of critical importance and is essential to preserving subject safety and the integrity of the study. Subjects who discontinue study drug must continue to be followed for collection of outcome and/or survival follow-up data as required and in line with [Section 5](#) until death or the conclusion of the study.

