3.6.1 Withdrawal of Consent

Subjects who request to discontinue study drug will remain in the study and must continue to be followed for protocol specified follow-up procedures. The only exception to this is when a subject specifically withdraws consent for any further contact with him/her or persons previously authorized by the subject to provide this information. Subjects should notify the investigator of the decision to withdraw consent from future follow-up **in writing**, if possible. The withdrawal of consent should be explained in detail in the medical records by the investigator, as to whether the withdrawal is from further treatment with study drug only or also from study procedures and/or post treatment study follow-up, and entered on the appropriate CRF page. In the event that vital status (whether the subject is alive or dead) is being measured, publicly available information should be used to determine vital status only as appropriately directed in accordance with local law.

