6 STUDY PERIODS, TREATMENT REGIMENS AND POPULATIONS FOR ANALYSES

6.1 Study Periods

The following periods are defined in this SAP for the purpose of analyses and reporting.

Screening period: Covers the time period which starts from the day of enrollment and lasts until the initiation of randomized double-blind treatment.

Treatment period: Starts at the time of the first dose of blinded treatment (BMS-986165 or placebo) and lasts until the date of the last dose of double-blinded treatment.

Follow-up period: Starts at the date of the last dose of blinded treatment and lasts 30 days post.

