7.5.1 Primary Efficacy Analysis

The algorithm for PASI scoring is provided in Section 8.1.1. The percentage change from baseline in PASI will be calculated using the following formula:

$$[(\text{PASI Score at Day 85} - \text{Baseline})/\text{Baseline}] * 100$$

For a subject, PASI-75 is 1 if the percentage change from baseline is less than or equal to -75%, i.e., the subject has greater than or equal to 75% improvement in PASI score comparing to baseline. Otherwise, PASI-75 is 0. Missing value for PASI-75 will be imputed and the imputation method is described in Section 8.3.1.

The following analyses will be provided:

- To compare the response rates between each treatment group and placebo, the PASI-75 at Day 85 will be analyzed by two-sample Fisher's exact test or Chi-square test based on the observed counts. The odds ratio (odds in treatment group/odds in placebo) and the

difference in the response rates and their corresponding two-sided 95% confidence intervals (CIs) will be provided.

There will be no adjustment for multiplicity. All comparisons will be performed in a pre-specified hierarchical procedure starting from the highest dose arm to the lowest dose arm. If a comparison is not significant at level 0.05, all p-values in subsequent comparisons will be considered nominal.

- For the primary efficacy endpoint, the proportion of subjects with moderate to severe psoriasis experiencing a 75% improvement in PASI score at Day 85 (PASI-75), the count and percentage of subjects with PASI-75, along with the 95% asymptotic and Clopper-Pearson exact two-sided CIs, will be provided in each treatment group.
- A logistic regression model analysis will be performed to evaluate the impact of treatments on PASI-75 at Day 85, with treatment group, age, gender, weight, BMI, baseline PASI score, use of previous biologic treatment, study region, and use of previous biologic treatment-by-study region interaction as covariates, if applicable.
- A bar chart of PASI-75 response rate at Day 85 by treatment group will be provided.

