8.5 Day Ranges for Analysis of Time Points

Subjects who do not always adhere strictly to the visit schedule timing in the protocol. Therefore, the designation of visits during the treatment period of the study will be based on the day of evaluation relative to the trial (day of first study medication = study Day 1) rather than the nominal visit recorded in the eCRF. Mutually exclusive relative day windows are defined below to provide derived visits that correspond to the post-baseline time points. If a visit falls outside of the pre-specified visit windows, then the data collected at that visit will not be assigned a derived visit but will remain in the derived data sets. Determination of baseline values is addressed in Section 8.2.

If a subject has more than 1 visit where a measurement is recorded within a window, the measurement closest to the target day will be used. In case of 2 visits being equidistant from the target, the earlier measurement will be used in analyses. For these safety indicators, the least favorable value (toward a positive response) in the window will be used.

Designation of visits for efficacy assessments during the treatment period is tabulated below.

Table 8.5-1: Day Ranges for Efficacy Assessments

Visit	Target Day	Days Range
Baseline/Day 1	1	1
Day 8	8	2-11
Day 15	15	12-22
Day 29	29	23-43 *
Day 57	57	44-71
Day 85	85	72-100

* DLQI is not assessed on Day 8 and Day 16. Days range for DLQI of Day 29 is 2-43.

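### SAP 8.3.1 has no explicit rule for other psoriasis therapy: a subject still on study drug who takes it and shows PASI-75 at Day 85 is scored a primary responder, and scoring after study drug is stopped is ambiguous

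*SAP*

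**What the plan says.** **Response.** SAP 7.5.1: "For a subject, PASI-75 is 1 if the percentage change from baseline is less than or equal to -75" percent, and 0 otherwise. Treatment status is not part of the definition.

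**Imputation.** SAP 8.3.1 opens with "If the response cannot be assessed due to missing data" or because of early discontinuation. It then gives two rules. The first is "Any subject who prematurely discontinues the trial during the treatment period after receiving study medication will have data imputed as non-responder at all scheduled" visits up to the end of the treatment period. The second sets any value that still cannot be determined to non-response.

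**Windows.** SAP 8.5 says "the designation of visits during the treatment period of the study will be based on the day of evaluation relative to the trial", and Table 8.5-1 gives Day 85 the range 72-100. SAP 6.1 says the treatment period "lasts until the date of the last dose of double-blinded treatment".

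**Follow-up.** Protocol 3.6: "Subjects who discontinue study drug must continue to be followed for collection of outcome" data. Protocol 3.6.1: "Subjects who request to discontinue study drug will remain in the study and must continue to be followed for protocol specified follow-up procedures". Protocol 5.3 and footnote a of Table 5.1-2 give subjects who end early a Day 85/early termination (ET) visit. Section 5.3 asks that it come soon after the last dose and before any prohibited medication.

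**Other therapy.** It appears in the SAP as a relevant protocol deviation: Appendix 1 lists prohibited treatment taken while on study therapy, by reference to protocol Table 3.4.1-1. Deviations lead to a per-protocol analysis at about 10% of subjects.

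**The concern.** Protocol 3.1 says that background therapy is withdrawn to learn whether the drug "exerts a potent anti-psoriatic effect in the absence of background therapy". A PASI-75 reached with the help of another psoriasis therapy does not answer that question, yet the scoring rule admits it. The direction of the error is not fixed: switching mainly on placebo shrinks the estimated effect, and switching mainly on an active dose inflates it. Estimates matter here because the five doses are tested in a hierarchy, and the trend and between-dose comparisons are secondary objectives.

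The second issue is reproducibility. If a subject stops study drug but stays in the trial, two programmers could follow the SAP and score the same primary endpoint differently.

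**Working it through.** **1. Other therapy while still on study drug.** The subject is in the trial, the treatment period is still running, and a PASI exists in Days 72-100. The response can be assessed, so neither rule of 8.3.1 applies, and 7.5.1 scores a 75% improvement as 1. The text leads to this result without ambiguity.

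**2. Study drug stopped, with or without a later switch.** Two readings are open.
- *Value used:* protocol 3.6 and 3.6.1 keep the subject in the study, so the subject has not discontinued the trial, and a PASI in Days 72-100 fills the window.
- *Non-response:* 8.5 assigns visits during the treatment period, which 6.1 ends at the last dose. A later PASI then gets no Day 85 visit, and the second rule of 8.3.1 makes it non-response. An ET visit on Days 72-84 may also be non-response if stopping drug is read as discontinuing the trial.

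The first rule of 8.3.1 also runs only to the end of the treatment period. Read with 6.1, it may reach no visit after the last dose. If the follow-up visit is made 30 days after the last dose, a last dose on Days 42-70 puts it on Days 72-100, with the same uncertainty.

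**3. Existing cover.**
- Appendix 1 does not reach therapy begun after the last dose.
- The status of the per-protocol analysis is inconsistent. SAP 6.3 reads as if the primary analysis is run on that population above 10%, 7.2.1 as an added analysis, and 7.5.6 makes it optional at 10% or more.
- With 6 x 42 = 252 subjects, 0.10 x 252 = 25.2, so 26 subjects are needed. That count pools all Appendix 1 deviations, so it cannot be judged from switching alone.
- The sensitivity analysis in 7.5.5 is optional and has no stated method. Its trigger leaves out discontinuation for lack of efficacy.

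**4. The plan's own figures** (SAP 5: 42 per arm, one-sided Fisher's exact test, 0.05). Exact binomial enumeration gives 99.97% for 60% vs 10% (stated: at least 99%). The minimum is 82.6% for a 30-point difference between active arms (stated: at least 82%). Both reproduce.

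**5. Illustration.** Assumed, not in the documents: active rate 35%, share switching s, share of switchers responding r = 0.5. The placebo rate of 10% is the plan's.
- Non-responder scoring: arm rate = p(1 - s)
- As observed: arm rate = p(1 - s) + r s
- Example, placebo, s = 0.05: 0.10 x 0.95 = 0.095; as observed 0.095 + 0.025 = 0.120

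| Switching | Non-responder: rates, power | As observed: rates, power |
|---|---|---|
| none | 35.0 vs 10.0, 82.1% | same |
| 2% both arms | 34.3 vs 9.8, 81.0% | 35.3 vs 10.8, 79.8% |
| 5% both arms | 33.25 vs 9.5, 79.4% | 35.75 vs 12.0, 76.2% |
| 5% placebo only | 35.0 vs 9.5, 84.0% | 35.0 vs 12.0, 73.8% |
| 5% active only | 33.25 vs 10.0, 77.1% | 35.75 vs 10.0, 84.0% |
| 15% both arms | 29.75 vs 8.5, 73.3% | 37.25 vs 16.0, 64.0% |

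Equal switching leaves the rate difference unchanged. At 5% in one arm it moves by r s = 2.5 points: 25.5 to 23.0 (placebo only) or 23.25 to 25.75 (active only). With r = 0.2 and 5% in both arms, power is 79.4% vs 78.0%.

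**6. Planned contrast.** With 60% active, the same switching patterns and 15% in one arm only, power is never below 99.1%. A harsher assumption (20% on placebo only, 80% of them responding) gives 94.1%.

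**7. False positives.** With both true rates at 10%, the test's exact size is 2.0%. As-observed scoring with active-only switching and r = 0.5 gives 4.2% at s = 5% and 7.6% at s = 10%.

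**The case against.** **Conduct rules limit the exposure.** Protocol 3.4.2 restricts new medication to investigator-prescribed use for specific events, after consulting the medical monitor. Section 3.5 requires study drug to stop if the subject cannot comply with the protocol, and 5.3 places the ET visit before prohibited medication. This stands as mitigation: fewer subjects should reach Day 85 on other therapy. None of these rules says how a value is scored when it happens.

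**Counting observed outcomes is a recognised strategy, and the sentence in protocol 3.1 justifies washout at entry rather than a scoring rule.** This is fair, so the point should not be put as a breach of the protocol. But the SAP does not state that it chose this strategy; the result follows from silence.

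**The magnitude is entirely assumed.** This stands. The model also lets switchers respond at their arm's rate had they not switched. If switchers come only from non-responders, the 15% both-arms comparison becomes 82% vs 75%, a gap of 7 points instead of 9, while the one-arm gaps do not shrink.

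**Stronger readings that the documents do not support.** A reader might infer that every PASI on Days 72-100 counts whatever the treatment status. Sections 8.5 and 6.1 may exclude values after the last dose, so the claim is firm only for subjects still on study drug. A reader might also infer that the deviation rules can never alter the primary analysis, but SAP 6.3 can be read to say that they do.

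**Conclusion.** The gap is real but narrow. For subjects still on study drug, the SAP as written counts a PASI-75 reached with another psoriasis therapy as a primary response. For subjects who stop study drug, the scoring is ambiguous and needs clarification; either choice is defensible.

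The size cannot be established, because the documents give neither switching rates nor response rates on other therapy. At an assumed 35% vs 10% with half of switchers responding, 5% switching costs about 3 points of power if equal in both arms. In one arm only, it moves power by about 10 points (placebo) or 7 points (active) and the rate difference by 2.5 points. At 2% in both arms the change is about 1 point.

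A reader might infer that the main efficacy conclusion is at risk. The planned 60% vs 10% contrast does not support that: power stays at 99% or above for switching up to 15% with half responding. The exposure lies in the effect estimates and the weaker doses. This is a cheap improvement, held with moderate confidence.

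**What to change.** **Main change, SAP 8.3.1.** For the primary analysis, score as non-responder from that point any subject who starts a psoriasis treatment prohibited on study before the Day 85 assessment. Appendix 1 already takes its list from protocol Table 3.4.1-1. That table is written as a washout before randomization, so the sponsor should confirm that it applies on study, including after the last dose. Prespecify as-observed scoring as a sensitivity analysis.

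**Clarification, SAP 8.3.1 and 8.5.** State whether a PASI taken after permanent study drug discontinuation, including an ET visit on Days 72-84, can fill the Day 85 window.

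**To be reconciled by the sponsor.**
- Protocol 3.6 and 3.6.1 against 5.3 and Table 5.1-2 footnote a, on follow-up after stopping study drug.
- The synopsis (Study Design and Key Inclusion Criteria), which excepts some topical steroids, against 3.1, which excepts only emollients. Which clinical rule applies is for the sponsor.
- SAP 6.3, 7.2.1 and 7.5.6, on the status of the per-protocol analysis.

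**Cost.** SAP wording, one derived flag and one extra analysis. Concomitant therapy (protocol 3.4.2) and dosing (SAP 7.4.2) are already captured on the CRF, so no new visits or data are needed. The drawbacks are that a few observed values are overwritten in the primary analysis, though the sensitivity analysis shows them, and that the protocol passages must be reconciled first.

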8.3.2 Imputation of Missing Data for Continuous Variables

For analyses of change from baseline in efficacy measures, missing values will be dealt with via the longitudinal repeated measures analysis assuming MAR (missingness at random).

For all safety (including laboratory measurements) and PK measures, missing values will not be imputed.

8.4 Missing, Unknown or Partial Dates

The BMS safety guidelines for conventions relating to the handling of missing or partial dates and the determination of appropriate default values in such cases (in particular, for concomitant medication dose start-dates and end-dates and AE onset dates) will be utilized.

The following conventions may be used for imputing partial dates for analyses requiring dates:

For missing and partial adverse event onset dates, imputation will be performed using the Adverse Event Domain Requirements Specification1.

For missing and partial adverse event resolution dates, imputation will be performed as follows (these conventions may change):

- If only the day of the month is missing, the last day of the month will be used to replace the missing day.
- If the day and month are missing or a date is completely missing, it will be considered as missing.

Missing and partial non-study medication domain dates will be imputed using the derivation algorithm described in 4.3.3 of BMS Non-Study Medication Domain Requirements Specification2.

For other partial/missing dates, the following conventions may be used:

- If only the day of the month is missing, the 15th of the month will be used to replace the missing day.
- If both the day and the month are missing, “July 1” will be used to replace the missing information.

- If a date is completely missing, it will be considered as missing.

The following conversion factors will be used to convert days to months or years: 1 month = 30.4375 days and 1 year = 365.25 days.

All statistical analyses will be carried out using SAS (Statistical Analysis System software, SAS Institute, North Carolina, USA) unless otherwise noted.

